4.12.3 Interim Pharmacokinetic Analysis to Support SRC Dose Escalation Decisions

Cohort PK analysis is the responsibility of the CPMS group. The SRC will review blinded PK data (only for dose escalation from Cohort 2 to Cohort 5 and from Cohort 5 to Cohort 6) before dose escalation. Concentration data will be obtained directly from the bioanalytical laboratory Charles River Lab as per data transfer agreement in a unblinded manner. Phoenix[®] WinNonlin[®] version 8.0 or higher will be used to create an analysis ready dataset to conduct non-compartmental analysis (NCA) and to generate plots and tables for the blinded cohort PK analysis report to be discussed in the dose escalation/safety meeting. QCed (not QAed) concentration data from the bioanalytical laboratory, as agreed upon in data receipt agreement (DRA), will be used for PK analysis. All concentrations prior

ALXN1910-HV-101

Statistical Analysis Plan

to the first measurable concentration will be set to 0 and all concentrations within the individual profile, and after the last measurable concentration in a profile will be set to missing to create an analysisdataset for non-compartmental analysis, as well as for creating tables and figures. Nominal time from dose or from start of infusion (not actual time) will be used to calculate PK parameters. PK parameters described in the SAP will be calculated as data permit. Linear-log trapezoidal rule will be used to calculate PK parameters. Individual linear and semi-log participant plots by dose group, and linear and semi-log arithmetic mean concentration (+/- SD) versus time plots will be created by dose group. Individual and summary concentration and parameters will be tabulated. Box plots of C_{max} and AUC or of dose normalized C_{max} and AUC may be plotted to visualize dose linearity and proportionality. No exclusions may be made to create descriptive summary tables. The blinded interim PK report will not reveal individual participant's treatment assignments. Anonymized individual and summary data will be reported in the interim PK report to maintain blinding. Alias numbers will be used in place of actual subject numbers to present individual PK data. Placebo data will not be included in the blinded interim PK report.

In the event of one or more missing samples (from the subjects on active treatment only), to keep the blind, these will be replaced with the mean value or mean and median values, respectively, of the available data at that sampling time point and summary statistics will be computed and reported in tables including these imputed samples. In case of one missing subject's profile (e.g. incomplete cohort of at least 7 subjects or in case of incomplete PK set of a subject (active or placebo) due to discontinuation), only data for a maximum of 5 subjects on active treatment will be provided to avoid unblinding. Parexel team will ensure the subject with the highest concentrations will not be removed.

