#### 4. STUDY DESIGN

# 4.1. Overall Design

This is a Phase 1, randomized, double-blind, placebo-controlled study designed to evaluate the safety, tolerability, PK, PD, and immunogenicity of SADs of ALXN1910 SC and a SAD of ALXN1910 IV in up to approximately 48 healthy adult participants across treatment cohorts (up to approximately 36 participants to receive ALXN1910 and up to approximately 12 participants to receive placebo) (Table 5).

Of the 48 participants, 8 will be of Japanese descent, defined as those participants whose parents and grandparents are both Japanese and who have spent less than 10 years outside of Japan. The inclusion of Japanese participants aims to meet the regulatory requirements of the ICH Guidance E5(R1), which provides a general framework for evaluating the potential impact of ethnic factors on the acceptability of foreign clinical data.

For this FIH study, 8 participants will be randomly assigned in a 3:1 ratio to treatment and placebo in each of the 6 cohorts with escalating doses of 5 mg IV (Cohort 1), 15 mg SC (Cohort 2), 15 mg IV (Cohort 3) in parallel with 15 mg SC in Japanese participants (Cohort 4) and 45 mg SC (Cohort 5), followed by 135 mg SC (Cohort 6). The first 2 participants randomized to each cohort will be dosed as a sentinel pair, with 1 participant on active treatment and 1 participant on placebo. This dosing strategy is justified given the large exposure margins (approximately 15-fold at the highest planned single dose of 135 mg SC).

At the discretion of the Investigator, up to 3 more participants will be dosed at least 48 hours (as anticipated tmax occurs prior to 48 hours postdose) after the dosing of the sentinel pair, followed by dosing of the remaining participants in the cohort no earlier than 72 hours after sentinel pair dosing, as long as no suspension/stopping criteria have been met. At no time will more than 4 participants per cohort be dosed in a given day.

Participants who meet the qualifications for the study based on screening will be admitted to the CRU the day prior to dosing (Day -1) to undergo Check-in assessments per the applicable SoA (Section 1.3).

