# 4.5. Duration of Treatment and End of Study Definition

[figure not shown]
Following a Screening Period of up to 28 days, there will be a Dosing and Follow up Period (single dose on Day 1 through the EOS Visit) of approximately 74 days.

Based on data from preclinical models, the half-life of ALXN1910 is expected to be approximately 7 days in healthy adult participants; therefore, the end of study visit is planned on Day 75, representing approximately 10 half-lives after initial study intervention administration. The total study duration per participant is approximately 103 days. An overview of the study visits is present in Figure 2.

A participant is considered to have completed the study if they complete all visits of the study including the last scheduled visit specified in the SoA (Section 1.3).

The end of the study is defined as the date the last participant completes the last visit (as specified in the SoA [Section 1.3]).

Figure 2: Overview of Study Visits

Abbreviation: D = day

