## 6.6. Dose Modification

Decisions to continue or modify dosing will be made by the Investigator and/or SRC after review of the blinded data as described in Table 8. The SRC may also make recommendations regarding safety issues, study conduct, or study suspension.

Predicted ALXN1910 human PK exposure (Table 6) indicates Cohort 5 or Cohort 6 mean projected PK exposure should not exceed 50% of the NOAEL exposure established in the 28-day GLP toxicology study in monkeys. In the event that mean PK exposure in Cohort 5 or Cohort 6 is predicted to exceed 50% of the NOAEL exposure, a lower dose will be selected so the above criteria can be met. PK data will not be used for dose escalation from Cohort 1 to Cohort 2 as greater than 150-fold PK (safety) exposure margin is expected for Cohort 2.

Dose escalation requires agreement between the Investigator and Alexion; Alexion may not supersede the Investigator if there are concerns that dosing should be stopped.

**Table 8:** Detailed Dose Escalation Criteria for Each Cohort

Dosing Decision	Responsible Party	Data to be Reviewed	Documentation/ Communication Methods
Dose escalation from Cohort 1 to Cohort 2	SRC	• At minimum, 14 days of postdose safety and tolerability data from at least 7 participants in Cohort 1.	The SRC will document the decision on the escalation/progression approval form.
Dose escalation from Cohort 2 to Cohort 5 (in parallel with Cohort 3 and Cohort 4)	SRC	
 
At minimum, 14 days of postdose safety and tolerability data from at least 7 participants in Cohort 2.
 
Seven days of PK data from at least 7 participants in Cohort 1 and at least 7 participants in Cohort 2.
 
	The SRC will document the decision on the escalation/progression approval form.
Dose escalation from Cohort 5 to Cohort 6	SRC	
 
At minimum, 14 days of postdose safety and tolerability data from at least 7 participants in Cohort 5.
 
Seven days of PK data from at least 7 participants in Cohort 5.
 
The cumulative PK data from Cohort 1 and Cohort 2.
 
	The SRC will document the decision on the escalation/progression approval form.

Abbreviations: PK = pharmacokinetic; SRC = Safety Review Committee

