%AUC _{ex}	The percentage of AUC _{0-inf} obtained by extrapolation will be calculated as follows: $%AUC_{ex} = \frac{AUC_{\infty} - AUC_{0-i}}{AUC_{\infty}} \times 100$. Unless otherwise determined by PK Scientist's best knowledge and judgment, if the %AUC _{ex} is greater than 30%, the value, %AUC _{ex} , will be flagged and all dependent parameters (ie, AUC _∞ , V _d /F and CL/F (SC) or V _d and CL (IV) will be flagged in listings and excluded from summary tables and statistical analysis of PK parameters, unless instructed otherwise by the Sponsor. In the case that $20\% \le %AUC_{ex}, \le 30\%$, the parameter together with all derived parameters will be flagged in listings. The reason for flagging/exclusion will be listed/footnoted in parameter listings.				
λz and t½	 The apparent terminal phase rate-constant (λz) will be estimated by linear regression of concentration versus time data presented in a log-linear scale. Data are primarily monotonically decreasing in magnitude and are representative of the actual decline in the log concentration-time curve. Only those data points that are judged to describe the terminal log-linear decline will be used in the regression. A minimum number of three data points in the terminal phase will be used in calculating λz with the line of regression starting at any post-C_{max} data point (C_{max} should not be part of the regression slope). Unless otherwise determined by PK Scientist's best knowledge and judgment or if instructed by the Sponsor, if the adjusted correlation coefficient (R² adjusted) is <0.8, then λz and all the λz dependent parameters (i.e. t¹/₂, AUC_∞, CL/F and V_d/F (SC admin.) or CL and V_d(IV admin) will be flagged in listings and excluded accordingly from summary tables and statistical analysis of PK parameters. %AUC_{ex} will be flagged, but not excluded. In the case of 0.8 ≤ R² < 0.9, λz and all the λz dependent parameter sitings. Unless otherwise determined by PK Scientist's best knowledge and judgment, the interval used to determine λz should be equal or greater than 1.5-fold the estimated t¹/₂, and if less than 1.5-fold, λz will be flagged in listings and might be excluded (based 				

CONFIDENTIAL

Statistical Analysis Plan

Parameter	Guideline for Derivation						

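### The interim PK report to the SRC summarises parameters with no exclusions, although 7 days of data on a drug with a half-life of about 7 days will usually not support AUC-infinity, half-life, CL/F or Vd/F for SC participants

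*SAP*

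**What the plan says.** **Interim rule (SAP 4.12.3).** For the SRC report, "PK parameters described in the SAP will be calculated as data permit". Individual and summary parameters are tabulated, and "No exclusions may be made to create descriptive summary tables". Optional box plots of Cmax and AUC, or of their dose-normalised forms, are offered for judging dose linearity and proportionality; the section does not say which AUC. The Table 3 flags are not mentioned.

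**Final-analysis rules (SAP 4.12.2, Table 3).**
- More than 30% of AUC-infinity extrapolated: AUC-infinity, CL (or CL/F) and Vd (or Vd/F) are flagged and, by default, excluded from summary tables. Between 20% and 30%: flag only.
- Adjusted R-squared below 0.8: lambda-z and everything derived from it, half-life included, are excluded by default.
- The regression interval for lambda-z "should be equal or greater than 1.5-fold the estimated" half-life. If it is shorter, lambda-z must be flagged. Excluding it and its dependents is discretionary.

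The only relaxation that SAP 4.12.2 itself gives for dose-escalation meetings is the use of nominal times.

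**Data required (Protocol 6.6, Table 8).** For Cohort 2 to 5: "Seven days of PK data from at least 7 participants in Cohort 1 and at least 7 participants in Cohort 2". For Cohort 5 to 6: "Seven days of PK data from at least 7 participants in Cohort 5", plus "The cumulative PK data from Cohort 1 and Cohort 2".

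**Kinetics.** Protocol 4.5 states that "the half-life of ALXN1910 is expected to be approximately 7 days in healthy adult participants". Protocol 4.1 anticipates a tmax that "occurs prior to 48 hours postdose".

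**The concern.** For its final tables the SAP treats AUC-infinity, CL and Vd as unfit to summarise when too much is extrapolated. At the interim, where the sampling window is shortest, the no-exclusion rule lets the same values into the summary tables. The rule does not cause the unreliability; the 7-day window does. What the rule does is remove the safeguard without a stated reason.

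The cohorts are small: six active participants, or at most five when a profile is missing (SAP 4.12.3). One participant with a flat fitted slope can move a mean AUC-infinity, half-life or clearance noticeably. The SRC reads these tables, and possibly box plots of an unspecified AUC, before escalation to 45 mg and to 135 mg.

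**Working it through.** **Inputs from the documents:** half-life 7 days = 168 h (Protocol 4.5); PK window 7 days = 168 h (Protocol Table 8); SC tmax before 48 h (Protocol 4.1); limits of 30% and 1.5 half-lives (SAP Table 3); predicted AUC0-168h and Cmax (Protocol Table 6). **Not in the documents, so assumed:** between-participant variability, residual error and the shape of the early decline.

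**1. The plan's own figure.** Protocol 4.3 equates 14 days with 2 half-lives: 14/7 = 2.0. This agrees with a 7-day half-life.

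**2. Extrapolated share at 168 h.**
- IV, one exponential: 2^(-168/168) = 50.0%.
- SC, first-order absorption at rate ka, with k = ln 2/168 = 0.00413 per h: the share is close to 0.5 × ka/(ka − k). For ka = 0.08 per h it is 0.0400/0.0759 = 53%; for ka = 0.05 per h it is 0.0250/0.0459 = 54%.

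All exceed 30%.

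**3. Longest possible regression interval.**
- IV: 168/168 = 1.0 half-life.
- SC, starting at 48 h: (168 − 48)/168 = 0.71 half-lives.
- Required: 1.5 × 168 = 252 h, which is longer than the window.

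**4. Half-life at which the rules would be met.**
- 30% rule, IV: 168 × ln 2/ln(1/0.3) = 96.7 h = 4.03 days or less.
- Interval rule: 168/1.5 = 112 h = 4.67 days or less (IV); 120/1.5 = 80 h = 3.33 days or less (SC from 48 h).

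**5. How many participants would fail.** Simulated non-compartmental analysis used the scheduled times to 168 h, 5% residual error and a 7-day terminal half-life.

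| Profile | Over 30% extrapolated, or R-squared below 0.8 | Any Table 3 criterion failed |
|---|---|---|
| One exponential, half-life CV 20–40%, SC | 93–98% (30% rule alone) | 95–100% (SC and IV together) |
| One exponential, half-life CV 20–40%, IV | 92–99% (30% rule alone) | 95–100% (SC and IV together) |
| Two exponentials fitted to Table 6, initial half-life 6 to 36 h, SC | 96% down to 42% | 99% down to 91% |
| Same, IV | 93% down to 6% | 98% down to 46% |

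The two-exponential rows matter because one exponential does not fit Table 6 for 15 mg IV: a Cmax of 3.39 (Table 6 rounds to 3.4) with a 7-day half-life gives 3.39 × (168/ln 2) × 0.5 ≈ 410, not 225.1. With a 36 h initial half-life, the error-free SC profile passes the 30% rule (26.9% extrapolated), but only because the fitted half-life is 3.2 days instead of 7; its regression interval is 0.94 half-lives and still fails.

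**6. Effect on a proportionality reading.** Take two exactly dose-proportional SC cohorts of six active participants (one compartment, half-life 168 h, no between-participant variability). The ratio of mean AUC-infinity should be 1. Its 5th–95th percentile range is about 0.80–1.22 at 5% residual error. At 10% it is 0.53–1.72 (ka 0.05) or 0.74–1.39 (ka 0.08); these wider ends depend on how terminal points are chosen. For AUC0-168h the ratio stays within about ±4%.

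**7. Could the 50%-of-NOAEL check change?** Table 6 gives AUC margins of 45 at 45 mg and 15 at 135 mg. To reach 50% of the NOAEL exposure, exposure must be 45/2 = 22.5 or 15/2 = 7.5 times the prediction. If AUC-infinity (about twice AUC0-168h) were wrongly used, with a single-profile error at the 95th percentile of 2.7-fold (15% residual error), the factor would be 2 × 2.7 = 5.4, still below 7.5.

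**The case against.** The best defence is that nothing makes AUC-infinity an escalation metric. Protocol 6.6 points to Table 6, whose margins are in AUC0-168h and Cmax, and AUC0-168h is already in SAP Table 2. The SRC includes a clinical pharmacologist and receives individual parameters and semi-log plots, so a flat slope would be visible. The phrase on calculating as data permit allows a parameter not to be derived, the wording on exclusions could be read as permissive, and not restating the flags is not the same as removing them. All this stands and limits the consequence. It does not remove the point: on its ordinary reading, the sentence puts values into summary tables that Table 3 would exclude, and the AUC in the box plots is left open.

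Four stronger readings are tempting, and the documents do not support them.
- *Nearly every participant fails.* This depends on unstated variability and profile shape. Table 6 implies a faster early decline than a simple one-compartment SC model: AUC0-168h/Cmax is 398.2/3.3 = 121 h and 1208.8/10.2 = 119 h, against about 135–138 h in that model. For IV Cohort 1 the rate is not secure.
- *Half-life would be excluded by default.* The 30% rule does not list half-life. The interval rule requires a flag on lambda-z and leaves exclusion to judgement; only a poor fit excludes half-life by default.
- *All interim data are limited to 7 days.* That is the minimum for the newly reviewed cohort. Cohort 1 and 2 data are cumulative at the Cohort 5-to-6 review, at least 14 + 14 = 28 days after their dosing. Day 15 samples should also exist by the 14-day safety review, although Table 8 does not require them for PK.
- *The NOAEL check could be decided wrongly.* Step 7 shows that the margins make this very unlikely.

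**Conclusion.** The point holds in a limited form. At the documents' own 7-day window and 7-day half-life, a typical participant in SC Cohorts 2 and 5 would have about 50% of AUC-infinity extrapolated and cannot reach a 1.5 half-life regression interval. In every SC scenario tried with a 7-day half-life, at least one Table 3 criterion failed in 91–100% of profiles. The share facing default exclusion is less certain, from 42% to 98%. These rates rest on assumed error, variability and profile shape, and on a half-life predicted from preclinical models; at a true half-life of about 3 to 4 days the failures would largely disappear.

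The practical risk is a misleading interim picture of dose proportionality, half-life and clearance before escalation. The final analysis, with sampling to Day 75 and the Table 3 rules in force, is not affected. The change is worth making because it is cheap and because the reliable measures, Cmax and AUC0-168h, are fully observed at 7 days.

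**What to change.** In SAP 4.12.3, state that:
- interim exposure summaries, the AUC box plots and the comparison with the NOAEL exposure use Cmax and AUC0-168h, with tmax and the dose-normalised forms;
- any AUC-infinity, half-life, CL or Vd shown carries the Table 3 flags and default exclusions.

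This also keeps cohorts with different lengths of follow-up on the same footing at the Cohort 5-to-6 review.

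The cost is SAP wording, with no change to sampling, timing or blinding. AUC0-168h is already in SAP Table 2; its dose-normalised form is not listed there and needs one added line. The downside is that the SRC sees fewer summarised parameters at the interim.

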4.12.4 Statistical Analysis of Pharmacokinetic Parameters

* Assessment of Absolute Bioavailability

The absolute bioavailability (F) for the ALXN1910 SC cohorts will be defined by the ratio of the geometric means for the area under the serum concentration-time curve from time 0 (dosing) to infinity parameter for the ALXN1910 SC cohort (cohort 2, 15 mg) over the ALXN1910 IV cohort (cohort 3, 15 mg).

A mixed effect model will be performed to the ln-transformed AUC_{∞} and the independent variables will include fixed effects for treatment and participant as a random effect. Geometric least-squares means for each treatment (SC or IV), point estimates and associated 95% CIs for the ratios for AUC_{∞} will be produced in tabular format. This will be anti-log transformed to obtain the point estimates and the 95% CI for the geometric mean ratio on the original scale. Estimates of between -participant variability (%CV) will also be provided.

SAS code for this analysis is mentioned in Section 6.5.

* Assessment of Dose Proportionality

Power model using linear regression method:

Dose proportionality will be assessed for sc cohorts, Non-Japanese only, for C_{max} and AUC (AUC_t, AUC_{∞}) using the PKAS who received single dose of ALXN1910 SC (Cohort 2, 5, and 6). PK parameters will be used to perform a LS linear regression analysis, using the formula ln_PK parameter =A× ln_dose + B, where 'ln PK Parameter' represents the natural log transformed C_{max} and AUC parameters and 'ln_dose' represents the natural log-transformed dose, A is the slope of the regression line and B is the intercept of the lines. The estimate obtained for A is a measure of dose proportionality.

Alexion Pharmaceuticals, Inc.	
ALXN1910-HV-101	Statistical Analysis Plan

An estimate of the slope and intercept of the regression line and corresponding 95% CI will be obtained for each PK parameter (C_{max} , AUC_t, and AUC_{∞}).

SAS code for this analysis is mentioned in Section 6.5.

Dose-proportionality based on the power model will be accepted ("not rejected", in terms of statistical inference) if the 95% CIs of the slope does not include 0 for each PK parameter.

Figure for Dose-Proportionality with 95% CI will be presented.

✤ Assessment of Ethnicity Comparison

The PK parameters for ALXN1910 will be evaluated for Japanese and non-Japanese participants (Cohort 2 versus Cohort 4) on active treatment, using an analysis of variance statistical model with cohort as the fixed effects on the natural logarithms of the data. In addition, the Japanese versus non-Japanese cohorts will be evaluated using descriptive statistics; for each cohort, the geometric means and the associated 95% CIs of difference of PK parameters will be reported.

PK parameters will be separately analyzed using a mixed effects model. The dependent variable will be the log-transformed PK parameters of interest (AUC $_{\infty}$, AUC_t and C_{max}) and the independent variables will include a fixed effect for ethnicity (Japanese vs non-Japanese) and participant as a random effect.

The estimated difference and CI obtained on the log scale will be exponentiated to provide an estimate of the Japanese to non-Japanese ratio and its associated 95% CI. Estimates of between -participant variability (%CV) will also be provided.

Plots of adjusted GMR of Japanese to non-Japanese together with 95% CIs will be produced.

SAS code for this analysis is mentioned in Section 6.5.

4.12.5 Pharmacodynamic Analysis, Concentration, and Parameter TFLs, and Statistical Analysis of Pharmacodynamic Parameters

Individual participant PPi versus time profiles values, both observed and change from baseline, will be calculated by Charles River Lab and Individual participant PLP, PL, PA versus time profiles values, both observed and change from baseline, will be calculated by PPD Laboratories respectively. Baseline observed, observed, change from baseline, and percent change from Baseline PPi, PLP, PL, PA versus time profiles values will be listed by treatment, sampling time and participant. Listings will include actual sampling times relative to dose administration, observed PPi, PLP, PL, PA versus time profiles value, change from baseline value, and percentage change from baseline. Baseline will be taken as the last measurement prior to dosing, see Section 6.1 Descriptive statistics (number, mean, SD, CV%, minimum, median, and maximum) will be presented by dose cohort, including pooled placebo, pooled active treatment across cohorts, pooled IV cohorts, pooled SC cohorts and overall for absolute, and percentage change from baseline PD assessment, time of minimum and time of maximum will only have minimum, maximum, and median time.

To visualize the comparison between participants and treatments the following descriptive PD graphs will be generated.

- Figure x.x.x: Overlaid Participant Profiles for PPi, PLP, PL, and PA Time Profile Data (Observed, Change from Baseline, and percent change from Baseline)
- Figure x.x.x: Mean (± SD) PPi, PLP, PL, and PA Time Profile Data (Observed, Change from Baseline, and percent change from Baseline)

Alexion Pharmaceuti	cals, Inc.				
ALXN1910-HV-101					Statistical Analysis Plan
			_		

For each figure, participants belonging to each category will be shown on the same plot with separate figures for each level of dose. Participant level figures will use actual time, while mean plots will use planned time, except for predose time point(s), where time 0 will be used rather than actual time.

